1. STUDY OBJECTIVES

1.1 Primary Objective

Primary Aim I: To recruit and retain adults with depressive symptoms into a controlled trial of hyperthermic yoga, randomizing 40 participants to each the immediate yoga group (IYG) and delayed yoga group (DYG; control group) with seventy-five percent retention in both groups.

Hypothesis 1a: Seventy-five percent of the each group will complete a week-8 assessment.

Hypothesis 1b: Acceptability of hyperthermic yoga will be high on the Acceptability Interview.

Primary Aim II: To collect the Inventory of Depressive Symptomatology – Clinician Rated (IDS-CR) scores at screening; baseline; and weeks-1, -3, -5 and -8 to evaluate the efficacy of hyperthermic yoga for depressive symptoms.

Hypothesis II: The IYG will have greater decreases in Inventory of Depressive Symptomatology – Clinician Rated (IDS-CR) scores after 8-weeks compared to the DYG.

Primary Aim III: To collect (a) physiological and (b) psychological mediators of hyperthermic yoga in the IYG and DYG group at screening; baseline; weeks-1, -3, -5 and -8 to evaluate treatment response in the IYG compared to the DYG.

Hypothesis IIIa: Salivary cortisol, and inflammatory markers (i.e., Tumor Necrosis Factor [TNF- α], Interleukin-6 [IL-6], and C-Reactive Protein [CRP]) will significantly decrease following 5- and 8-weeks of hyperthermic yoga in the IYG compared to the DYG.

Hypothesis IIIb: Perceived stress, mindfulness, and rumination will improve by 5- and 8-weeks in the IYG compared to the DYG.

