6.2.2 Enrollment, Baseline, and/or Randomization

Enrollment

Enrollment is defined as the date all of the screening criteria are met— occurring between screening (visit 1) and baseline (visit 2).

Baseline Assessments (Visit 2 for IYG; Visits 2 and 7 for DYG)

At this visit subjects will meet with a study clinician for a 50-minute psychoeducational (see First Heated Yoga Class: What to Expect) and motivational session. Subjects will be asked to discuss reasons for wanting to try the hyperthermic yoga and also to discuss potential barriers to participation.

Visit 2: Baseline - IYG and DYG

- IDS-CR
- HAM-D-28
- Self-Rated Questionnaires: STAI, SF-36, Q-LES-Q, EIFI, PSS, PSQI, FFMQ, RRS, URICA
- Concomitant Medications
- Vital Signs
- Psychoeducational Session
- Waist-to-Hip Ratio
- Physiological Markers (i.e., inflammatory markers [blood], cortisol [saliva])
 - Please see section 9.5.2 for details
- Collect Sleep Diary (can bring to the following visit as long as it was completed for the right week)
- Collect salivates (can bring to the following visit as long as it was collected at the right time period)
- Adverse Events
- Hot Yoga Beliefs Scale

Visit 7: Repeat Baseline - DYG

- IDS-CR
- HAM-D-28
- Self-Rated Questionnaires: STAI, SF-36, Q-LES-Q, EIFI, PSS, PSQI, FFMQ, RRS, URICA
- Concomitant Medications
- Vital Signs
- Psychoeducational Session (refresher)
- Waist-to-Hip Ratio
- Physiological Markers[^] (i.e., inflammatory markers [blood], cortisol [saliva])
- Collect Sleep Diary (can bring to the following visit as long as it was completed for the right week)
- Adverse Events

- Hot Yoga Beliefs Scale

[^]If this visit takes place within 14 days of Visit 6, Physiological Markers will not be repeated at this visit.

At the end of the Baseline Visit that occurs before they start the yoga (V2 or V7), participants will be handed a packet of self-rated questionnaires (i.e. STAI-State and EIFI) to complete within 30 minutes prior and 30 minutes post each yoga class they attend. We will ask participants to note time and date on the top of each form. These questionnaires will provide data on acute mood changes pre- and post-yoga. [name] co-mentor [name] uses these questionnaires to gather the same data in her RO1 (5R01AT007483-05). Including this will allow us to compare data across studies.

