6.2.5 Completion/Final Evaluation

Visit 6: Study Primary Endpoint (Week-8) for IYG and DYG (repeated for DYG in Visit 11 as 9-week Yoga Assessment)/Early Discontinuation Visit – IYG and DYG

- Physical Examination
- Habits Questionnaire
- C-SSRS since Last Visit
- IDS-CR
- HAM-D-28
- Self-Sated Questionnaires (STAI, SF-36, Q-LES-Q, EIFI, PSS, PSQI, FFMQ, RRS, URICA)
- Concomitant Medications
- Vital Signs
- Waist-to-Hip Ratio
- Physiological Markers (i.e., inflammatory markers [blood], cortisol [saliva])

- Collect Sleep Diary (can bring to the following visit as long as it was completed for the right week)
- Adverse Events
- Hot Yoga Beliefs Scale
- Acceptability Interview (completed at Visit 11 for DYG)
- MINI Mood Module

Final Evaluation: 1-Month Follow-Up Post-Yoga Visit – IYG (Visit 7) and DYG (Visit 12)

- Physical Examination
- Habits Questionnaire
- C-SSRS since Last Visit
- IDS-CR
- HAM-D-28
- Self-Rated Questionnaires (STAI, SF-36, Q-LES-Q, EIFI, PSS, PSQI, FFMQ, RRS)
- Concomitant Medications
- Vital Signs
- Waist-to-Hip Ratio
- Physiological Markers (i.e., inflammatory markers [blood], cortisol [saliva])
- Collect Sleep Diary
- Adverse Events
- Hot Yoga Beliefs Scale
- MINI Mood Module

Potential Reasons for Early Termination

Subjects can be potentially dropped from the intervention due to: 1) adherence to yoga or assessment visits, 2) being deemed unsafe to continue the yoga intervention, 3) worsening of depressive symptoms, or 4) suicide risk.

Please see section 8 (Intervention Discontinuation) for operational definitions of the above.

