9.2 Sample Size and Randomization

Sample Size and Power Estimation: Although this study will test for statistical significance, the primary aim of this pilot RCT is to estimate the intervention's effect size to conduct a more definitive R01 study, as is outlined in NIH guidelines for developing behavioral interventions³³. The study was powered conservatively based on an 80% (n=64) ITT sample. Effect sizes for the degree of change in IDS-CR (primary outcome) were estimated for the hyperthermic yoga versus the control using Cohen's d (effect size for t-test). A power analysis found that with an ITT sample of 64 (32 per arm), a two-tailed t-test with an alpha level of .05 will yield a statistical power of 79% to detect a large effect size of .70 and 50% to detect a moderate effect size (.50). Thus, if the effect size falls between moderate and large, power would approach 80%, since the evaluable sample should be between 64 and 80. Preliminary data suggested a moderate effect size of .54 for depression³⁴. We predict a more robust effect size of at least .60-.70, as this is a larger sample recruited specifically for depressive symptoms.

Randomization: Our biostatistician will establish the blind and deliver it to the designated Research Coordinator. Randomization will be done by random permuted block design in blocks of 2 and 4. This method assigns subjects to each intervention group with equal probability, while at the same time generating a balanced design. The random permuted block randomization method also protects against bias due to temporal trends (e.g., experience of research staff, or seasonal effect). This randomization design should balance the heterogeneity of the subjects between groups.

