9.3 Definition of Populations

A completer will be defined as a subject who attends: 1) a screen, 2) baseline, 3) at least one midpoint assessment (week-1, -3, or -5), and 4) a week-8 assessment visit. We will complete two analyses: 1) a completer analysis and 2) a modified ITT (MITT) analysis. The MITT will include those who have attended at least one post-baseline assessment visit. Our primary analyses utilize data from the IYG and DYG prior to the crossover.

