9.6 Data Analyses

Statistical Analyses: Analyses will be conducted using SPSS. Full descriptive data will be produced. Baseline differences between the yoga and control group (demographic variables and depressive severity) will be assessed and controlled for as necessary. Two analyses will be completed: 1) an MITT and 2) a "completer" analysis. Primary analyses will only include data from the IYG and DYG prior to the crossover. We will conduct exploratory analyses including crossover DYG subjects to increase power.

Missing Data: We will test whether missing data occurred randomly across conditions, in which case it will be handled by replacing data with the scale or sub-scale mean. Where this is not feasible, missing data will be imputed through maximum likelihood estimation or multiple imputation. If missing data is not random, advanced statistical analyses taking into account assumptions of various tests will be conducted.

Adherence: number of heated yoga classes attended will be used as a covariate in the efficacy analyses to determine if participants who go to more classes demonstrate greater improvement in depressive symptoms.

Primary Aim I: To recruit and retain adults with depressive symptoms into a controlled trial of hyperthermic yoga, randomizing 40 participants to each the immediate yoga group (IYG) and delayed yoga group (DYG; control group) with seventy-five percent retention in both groups.

Hypothesis 1a: Seventy-five percent of the each group will complete a week-8 assessment.

Hypothesis 1b: Acceptability of hyperthermic yoga will be high on the Acceptability

Interview.

Screening logs will reveal the proportion of eligible screened individuals enrolled in the study. We will track factors that make participants ineligible or unwilling to participate. The goal is 75% retention, with enrollment defined as completing at least one post-baseline assessment visit. Attendance data will be characterized descriptively and compared between treatment arms by chi-squared analysis. Yoga attendance will be examined as a potential covariate in subsequent analyses. Participants who participated in Yoga will be re-contacted at completion of all patient study interventions for accuracy of Yoga attendance. Patient's will be contacted up to three times before they will be labeled as "Lost to Recontact" in the screening logs.

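### Section 9.6 ties the 75% retention goal to a definition of enrollment that contradicts section 6.2.2 and, if used as the denominator, departs from Aim I and can only leave retention equal or raise it

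*Combined protocol and SAP*

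**What the plan says.** Primary Aim I (section 1.1, repeated in 9.6) plans to randomise 40 participants to each arm "with seventy-five percent retention in both groups". Hypothesis 1a supplies the numerator and the base: "Seventy-five percent of the each group will complete a week-8 assessment".

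The analysis paragraph for this aim in section 9.6 opens with "Screening logs will reveal the proportion of eligible screened individuals enrolled in the study" and, after a sentence on tracking ineligibility and unwillingness, continues: "The goal is 75% retention, with enrollment defined as completing at least one post-baseline assessment visit".

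Enrollment is defined elsewhere. Section 6.2.2 says "Enrollment is defined as the date all of the screening criteria are met" and places that date between visits 1 and 2. Section 3 gives a target enrollment of 160, meaning the number needed for screening in order to randomise 80.

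The condition used in 9.6 is the one that section 9.3 sets for the modified intention-to-treat population: "The MITT will include those who have attended at least one post-baseline assessment visit".

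Section 6.2.5 gives Visit 6 two roles: "Visit 6: Study Primary Endpoint (Week-8) for IYG and DYG (repeated for DYG in Visit 11 as 9-week Yoga Assessment)/Early Discontinuation Visit". Section 8 invites participants discontinued from the intervention to that visit.

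**The concern.** One term has two incompatible definitions and a third informal use. Randomisation comes at the end of the baseline visit (6.2.2), so enrollment under 6.2.2 precedes it and enrollment under 9.6 follows it. The two definitions count different people, and no section reconciles them.

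The 9.6 definition also sits in the sentence that sets the retention goal. A percentage needs a base, and this is the only one that the analysis paragraph offers. Used that way, it removes randomised participants who never attended a post-baseline visit, whereas Aim I and Hypothesis 1a point to everyone randomised. The protocol itself expects some early loss: section 3 reports that dropouts in the cited hyperthermic yoga trial tended to leave after one or two sessions.

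Retention in both groups is the stated target of Primary Aim I in a feasibility and acceptability pilot. Under this reading the target could be declared met with fewer than 75% of an arm retained.

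There is a smaller gap in the numerator. Visit 6 is both the week-8 and the early-discontinuation visit, and the plan does not say that an early exit visit is not a week-8 assessment.

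**Working it through.** **Inputs from the documents.** 40 randomised per arm and a 75% target in each arm (1.1, 9.6); dropout of 11.5% in the cited Bikram trial (2.2).

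**Assumed inputs.** The documents do not say how many participants will have no post-baseline visit. I take counts of 0 to 8 per arm, total losses of 20%, 25% and 30% beside the quoted 11.5%, and a share of losses before any post-baseline visit of 0, a tenth or a quarter.

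**The plan's own figures.** The target on all randomised is 0.75 × 40 = 30 per arm. The only computed design figures are those for power in 9.2. With 32 per arm and two-sided alpha 0.05, the noncentral t gives 78.7% at d = 0.70 and 50.4% at d = 0.50, against the stated 79% and 50%. They reproduce, and this point does not depend on them.

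**Direction.** Let W be the number completing week 8 in an arm and k the number randomised with no post-baseline visit. Week 8 is itself a post-baseline visit, so W is the same on both bases. Retention is W/40 on all randomised and W/(40 − k) under 9.6. Since 40 − k ≤ 40, the second is never smaller, and the two are equal when k = 0. Example: 27 completers are 27/40 = 67.5%, below target; with k = 4 they are 27/36 = 75.0%, on target.

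**Completers needed** = 0.75 × (40 − k), rounded up:

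| k | Base | Needed | As % of 40 |
|---|---|---|---|
| 0 | 40 | 30 | 75.0 |
| 1 | 39 | 30 | 75.0 |
| 2 | 38 | 29 | 72.5 |
| 4 | 36 | 27 | 67.5 |
| 6 | 34 | 26 | 65.0 |
| 8 | 32 | 24 | 60.0 |

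**Expected rate.** With total loss L and early share s, the expected rate under 9.6 is about (1 − L)/(1 − L·s). At L = 0.25 this is 0.75/0.975 = 76.9% for s = 0.10 and 0.75/0.9375 = 80.0% for s = 0.25, against 75.0% on all randomised.

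**Chance that both arms pass.** Each of 40 participants independently has no post-baseline visit (probability L·s), is lost later (L(1 − s)) or completes week 8 (1 − L). The arm passes if W ≥ 0.75 × base. The arms are independent with equal total loss, so the two pass probabilities multiply. The last two columns use s = 0.25.

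| Total loss | All randomised | Early loss in yoga arm only | Early loss in both arms |
|---|---|---|---|
| 11.5% (quoted) | 99.1% | 99.4% | 99.8% |
| 20% (assumed) | 70% | 79% | 88% |
| 25% (assumed) | 34% | 46% | 63% |
| 30% (assumed) | 10% | 18% | 32% |

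For 25% loss, one arm passes with probability 0.584 on all randomised and 0.793 under 9.6. So 0.584² = 0.34, 0.584 × 0.793 = 0.46 and 0.793² = 0.63. With a tenth of losses early in both arms, the chance is 99.3% at 11.5% loss and 41% at 25% loss.

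**The case against.** Section 9.6 never calls its definition a denominator. The paragraph opens with the proportion of eligible screened people who enrolled, and the clause may have been meant to explain that. Aim I and Hypothesis 1a, restated just above, already give a numerator and a base. This stands: the denominator reading is not the only one. It does not remove the conflict with 6.2.2, because the screening-log proportion would then have two definitions.

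Early loss may also be rare. The first post-baseline visit is at week 1 and may be held by phone, waitlist participants are paid for it, and those who stop yoga are still invited to Visit 6. Stopping classes is not the same as having no assessment, and section 3 gives dropout in sessions, not weeks. Waitlist participants attend no classes before week 8, so the reported pattern of leaving after one or two sessions cannot be carried over to them. This too stands. It is why early loss in both arms is only an upper scenario.

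A reader might go further and infer from "The study was powered conservatively based on an 80% (n=64) ITT sample" that the plan expects 8 participants per arm without a post-baseline visit, so that 24 completers would be enough. The documents do not support that: 9.2 does not say that its sample is the modified population of 9.3, nor when the missing 20% are lost.

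On Visit 6, the words of Hypothesis 1a already tell against counting an early exit. A cut-off at the edge of the visit window would be too rigid, because 6.2.4 lets staff hold visits outside the window of 3 workdays either side.

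**Conclusion.** The contradiction between 6.2.2 and 9.6 is certain and needs no interpretation. The effect on retention is conditional. It arises only if the 9.6 clause is used as the denominator, and only if some randomised participants have no post-baseline visit. Its direction is then fixed: the reported rate stays equal or rises.

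The size is small in the setting that the protocol documents: at 11.5% dropout the chance that both arms pass moves from 99.1% to between 99.3% and 99.8% across the two early shares, with early loss in both arms. It becomes material only if losses are well above that rate and a noticeable share come before any post-baseline visit, as in the 25% row. Those losses and shares are my assumptions, and the probabilities also assume independent participants and equal total loss in the two arms.

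A reader might infer that the plan has replaced its randomised base with the modified population, or that the efficacy result is compromised. Neither follows. The wording permits another reading, the efficacy analysis does not use this definition, and no stopping or progression rule depends on the 75% goal. The point is minor.

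**What to change.** - In 9.6, define retention in each arm as participants completing the week-8 assessment divided by all participants randomised to that arm.
- Delete the enrollment clause from the sentence on the 75% goal, or relabel it as the modified intention-to-treat criterion of 9.3. Keep the 6.2.2 definition of enrollment.
- In section 3, describe the 160 as the number to be consented or screened, so that enrollment has one meaning throughout.
- Report the rate among those with at least one post-baseline visit only descriptively.
- State that a Visit 6 held because of early discontinuation does not count towards Hypothesis 1a, whereas a scheduled week-8 assessment does, including one rescheduled as 6.2.4 allows.

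The cost is wording only, with no new data. The reported retention may be slightly less favourable.

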5.4 Adherence Assessment

Participants are asked to attend at least two weekly hyperthermic yoga classes over an 8-week intervention, a minimum total of 16 yoga classes. Adherence will be defined at 75% of the minimum prescribed dose of the study intervention – i.e., adherence means that participants attended at least 12 out of 16 yoga classes over the 8-week study intervention period. The two yoga studios track attendance via computer systems. Attendance data will be collected by study staff (usually a research assistant) who will either email via Send Secure email, or utilize Dropbox to communicate with the studio owners, [name] (Bikram Yoga Boston) and [name] (Bikram Yoga Cambridge), to obtain attendance data. All yoga students, whether study participants or not, are required to sign in at the front desk of the studios prior to class.

Yoga instructors act as front desk attendants for their own classes and sign participants into the computer system at this time.

Fidelity Assessment: The adherence of each of the two Bikram Yoga studios to the Bikram Yoga protocol will be established, prior to starting the proposed study and every six months thereafter with an adherence measure designed by [name].

Temperature Measurement: We will measure the temperature and humidity in the three heated yoga rooms with HOBO Bluethooth Low Energy Temperature/Relative Humidity Data. HOBO MX1101 data logger measures and transmits temperature and relative humidity data wirelessly to mobile devices via Bluetooth Low Energy (BLE) technology. These devices will be mounted in each of the three rooms. Study staff will collect data prior to study initiation and quarterly thereafter to monitor temperature and humidity- and to store the data for later analyses. These devices provide wireless and time stamped temperature and humidity data to smart phone device. The self-contained wireless data logger works with Onset's free HOBOmobile app for logger setup and data management. Data is accessible anytime from a mobile device for iOS or Android over a 100-foot range.

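### The one test named for Primary Aim I, a between-arm chi-squared on attendance, is empty if attendance means yoga classes and does not address the per-arm 75% level if it means visits

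*Combined protocol and SAP*

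**What the plan says.** Section 1.1 states Hypothesis 1a as a level to be reached in each arm: "Seventy-five percent of the each group will complete a week-8 assessment". Section 9.6 repeats it, with a design of "randomizing 40 participants to each the immediate yoga group (IYG) and delayed yoga group".

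The Aim I analysis text in section 9.6 then offers three things:

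- screening-log proportions;
- a retention target: "The goal is 75% retention, with enrollment defined as completing at least one post-baseline assessment visit";
- one inferential method: "Attendance data will be characterized descriptively and compared between treatment arms by chi-squared analysis".

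It gives no interval for retention and no rule for reading a result against 75%. The same section restricts the main comparisons: "Primary analyses will only include data from the IYG and DYG prior to the crossover".

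The Aim I text does not define attendance. Section 5.2 says the research assistant obtains attendance data from the studios. Section 5.4 says "The two yoga studios track attendance via computer systems" and sets the adherence cut-off: "adherence means that participants attended at least 12 out of 16 yoga classes over the 8-week study intervention period". In section 9.3, however, the verb attend refers to assessment visits.

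Enrollment also has two meanings. Section 6.2.2 has "Enrollment is defined as the date all of the screening criteria are met", whereas the retention goal in 9.6 counts only people with a post-baseline visit.

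**The concern.** A chi-squared between arms asks whether two proportions are equal. Hypothesis 1a asks whether each proportion reaches a fixed level. These are different questions, and the answer to one says nothing about the other.

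On the class-records meaning there is a further problem. In the first eight weeks the DYG is on the waitlist and is offered no study yoga, so one side of the comparison is fixed at zero by the design. Bringing in the DYG's later classes would avoid the zero. It would also compare different calendar periods, and in the DYG only people who stayed through the waitlist.

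Retention belongs to a primary aim of a feasibility pilot. A reader planning the larger study needs the retention rate in each arm, how precisely it is known, and whether the arms differ. The stated analysis supplies a p-value that bears on none of the first two, and a bare percentage.

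**Working it through.** **Inputs.** 40 randomized per arm and the 75% level (sections 1.1 and 9.6); adherence at 12 of 16 classes (5.4); pre-crossover data only (9.6). The plan gives no calculated figure for Aim I. Its only power figures (section 9.2) concern IDS-CR under Aim II and have no bearing here. The counts and true retention rates below are assumed scenarios.

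**1. Chi-squared on yoga classes before crossover.** For a/40 against b/40, the uncorrected Pearson statistic is 80 × [a(40 − b) − b(40 − a)]² / [40 × 40 × (a + b) × (80 − a − b)]. With 10/40 adherent in the IYG and 0/40 in the DYG:

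80 × (400 − 0)² / (1600 × 10 × 70) = 12,800,000 / 1,120,000 = 11.43, p = .0007 (Fisher .001).

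Even 6/40 against 0/40 gives p = .011 (Fisher .026). Adherence of 25% or 15% is poor, yet both results are significant because the DYG was not offered classes.

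**2. Chi-squared on visit completion.** Same formula, set against the 75% level:

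| Completers | Percent | p (uncorrected) | Against 75% |
|---|---|---|---|
| 24/40 v 24/40 | 60 v 60 | 1.00 | both miss |
| 38/40 v 30/40 | 95 v 75 | .012 | both meet |
| 30/40 v 24/40 | 75 v 60 | .15 | one meets, one misses |

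For the second row: 80 × (380 − 60)² / (1600 × 68 × 12) = 8,192,000 / 1,305,600 = 6.27.

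The p-value does not follow the hypothesis in either direction. As a check for differential attrition the test is legitimate but weak. Enumerating all tables at 40 per arm, two-sided .05, power is 55% for true rates of 85% v 65% and 37% for 85% v 70%.

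**3. What 40 per arm can say about 75%.** The exact (Clopper-Pearson) 95% CI uses beta quantiles: the lower limit is the 2.5% point of Beta(x, n − x + 1) and the upper is the 97.5% point of Beta(x + 1, n − x). For x = 30 and n = 40 this gives 58.8% to 87.3%. The lower limit first passes 75% at 36/40 (76.3%); at 35/40 it is 73.2%.

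Read as a point benchmark, the chance that one arm shows at least 30/40 is the binomial tail. Both arms must pass, so it is squared:

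| Assumed true retention | One arm | Both arms |
|---|---|---|
| 75% | .584 | .584² = .34 |
| 80% | .839 | .839² = .70 |
| 85% | .970 | .970² = .94 |

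**4. Denominator.** Suppose 32 of 40 in an arm have a post-baseline visit (assumed). Then 24 completers are 24/32 = 75% on the retention wording of 9.6, but 24/40 = 60% of those randomized.

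**The case against.** The plan never assigns the chi-squared to Hypothesis 1a. Retention has its own sentence with a 75% goal, and section 9.6 promises full descriptive data. An observed percentage set against a stated goal is an ordinary feasibility answer in a pilot and needs no test. This stands: the plan is not silent on Hypothesis 1a. What it lacks is the interval, a settled denominator and a statement of how the percentage will be read.

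Attendance in the disputed sentence may also mean visits. The sentence before it concerns assessment visits, and the one after it says yoga attendance explicitly, as if to mark a change of subject. On that reading the test is a normal check for unequal drop-out. This also stands in part: the term is ambiguous. But where the protocol speaks of collecting attendance data, in sections 5.2 and 5.4, it means studio records, so the class reading cannot be set aside. The visit reading still leaves the 75% level unaddressed.

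Three stronger inferences are tempting, and the documents support none of them:

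- That retention is a go/no-go rule for the larger trial. No section sets one. Section 9.2 names estimating the effect size as the pilot's main purpose, and the 75% in section 12 concerns recruitment.
- That 80% is the planned week-8 retention. In section 9.2 it is the size of the ITT sample used for the Aim II power calculation.
- That the lower confidence limit must clear 75%, which would need 36/40. Hypothesis 1a and the goal in 9.6 are worded as a benchmark, not as a level to be exceeded with stated confidence.

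**Conclusion.** The point holds in a limited form. If attendance means class records, the between-arm chi-squared on pre-crossover data has no content, because the control count is zero by design. This assumes that only study classes are counted and not yoga taken elsewhere. If attendance means visits, the test can detect only large differences between arms and does not bear on the per-arm 75% level. On either meaning, Hypothesis 1a is left with a descriptive goal, no interval and an unsettled denominator.

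The size is set by the sample: an observed 75% in an arm of 40 is compatible with true retention from 59% to 87%. The change is worth making because it concerns a primary aim. The gap is a mismatched test and a missing interval, not a wrong efficacy result.

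**What to change.** Reword the Aim I analysis in section 9.6 as follows.

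- **Hypothesis 1a.** Report week-8 completion in each arm out of all randomized (40 per arm), not only those with a post-baseline visit, with an exact 95% CI. Read the point estimate against the 75% benchmark (at least 30/40 in each arm) and present the CI as its precision.
- **Differential attrition.** Give the between-arm difference in week-8 completion with its 95% CI.
- **Yoga classes.** Define attendance. Describe the number of classes and the share meeting the protocol's own cut-off of 12 of 16, with an exact CI, within each arm's own 8-week yoga period. Drop the between-arm chi-squared on class attendance.
- **Enrollment.** Reconcile the definitions in sections 6.2.2 and 9.6, so that the retention denominator is unambiguous.

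The cost is a paragraph of wording and a few lines of analysis, with no new data and no change in conduct. The drawback is that the intervals will look wide at 40 per arm.
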